#### Antenatal health

- Smoking cessation during pregnancy [vital records data]
  - We will consider an enrollee to have ceased smoking during pregnancy if their vital record indicates that they smoked pre-pregnancy and that they did not smoke during pregnancy.
- Recommended gestational weight gain [vital records data]
  - Gestational weight gain will be classified as “recommended” if it is within the guidelines published by the National Academy of Medicine (formerly the Institute of Medicine).

The guideline-recommended antenatal care services should be received at the appropriate gestational age during the pregnancy. The gestational age at the time of the test will be calculated as the date of the test minus the approximate date of last menstrual period (in days). We will approximate the enrollee's date of last menstrual period using the child's date of birth and obstetrician's estimate of gestational age at delivery from the vital records. If these fields are missing, we will define the approximate date of last menstrual period as the beginning date of the index pregnancy (defined above).

Each of these outcomes can only be measured among pregnancies that reach the gestational age at which the care is recommended. The main analyses will only include pregnancies that last at least as long as the gestational age recommended for each outcome. However, it is possible that NFP has a direct effect on gestational age, which would mean that the sample of mothers observed could differ across treatment and control arms. If that is the case (i.e., if gestational age at birth between treatment and control group is statistically significantly different), then we will conduct a bounding exercise as a robustness check for the guideline-concordant care outcomes. Using Group B Strep as an example, the main analysis will compute the average treatment effect (ATE) among people whose pregnancies last at least 35 weeks. If gestational age is statistically significantly different between control and treatment arms, we will estimate two bounds on this ATE: (1) a recalculated ATE assuming *all* people who

did not reach 35 weeks' gestation would have received the test, and (2) a recalculated ATE assuming *none* of the people who did not reach 35 weeks' gestation would have received the test.

Table 1.3. Codes for analyses of antenatal care utilization and quality

	CPT/HCPCS	NDC	ICD-10

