#### **2.1. Defining the Sample for Analysis**

Our sample for analysis of our primary child-health related outcome will be restricted to mother-baby dyads with an identified index birth as defined in section A.1 of the pre-analysis plan. All analysis will take place at the mother level, where randomization occurs. We discuss how outcomes will be operationalized in the case of multiple births below. We will not restrict the sample based on matching to Medicaid data as the outcomes include utilization that will be observable in all-payer hospital discharge data. For outcomes that rely primarily on Medicaid data (i.e. outcomes related to preventive child health utilization), we may restrict the sample to mother-baby dyads where children retain either partial or continuous Medicaid coverage through the child's first or second year of life. We anticipate that the children of most mothers who enroll in the trial will be eligible for Medicaid for their entire first year of life but we anticipate that more children may drop off of Medicaid during their second year of life, whether because of the need to document eligibility or because of changes in eligibility in the second year of life during some periods of the study (see Table 2). We discuss the potential differences in Medicaid enrollment between control and treatment arms and planned sensitivity analyses and alternative specifications in section 2.4.

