### **3.5. Endogeneity of Outcome Data and Sensitivity Analyses**

Because outcomes related to contraceptive uptake will rely primarily on Medicaid claims data, we cannot observe contraception use in outpatient settings among women who are not enrolled in Medicaid. As a non-expansion state, all women with Medicaid pregnancy coverage in South Carolina, except undocumented and recent immigrants, retain Medicaid coverage for at least 60 days following childbirth. Women who qualify for other payment categories (e.g. foster-care, disability), may retain coverage past 60 days. Because NFP may affect maintenance of Medicaid coverage past 60 days postpartum, including maintenance of enrollment in Medicaid Family Planning coverage, we may not be able to observe treatment and control group mothers in the Medicaid claims data at equal rates.

To determine whether continuous Medicaid coverage differs between treatment groups, we will first compare continuous Medicaid coverage of any type (coverage through the low-income families, qualified disabled workers, pregnancy and family planning eligibility pathways), and

family planning Medicaid coverage specifically, between treatment and control groups at the three contraception outcome time points (6 weeks, 12 and 24 months). Continuous coverage will be measured using Medicaid enrollment data and will be defined as enrollment during all months, starting with the month of childbirth through 6 weeks, 12 and 24 months postpartum. It is also possible that while average Medicaid enrollment will not differ between the two groups, the type of women retaining coverage will be affected by NFP. Therefore, using a joint F-test, we will also test whether there are differences in the characteristics of participants between control and treatment groups enrolled in Medicaid during the three-outcome time points (60 days, 12 months, 24 months).

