When conducting the study analysis, we will divide outcomes between those that we observe within 60 days after childbirth (when nearly all women retain Medicaid), and those measured after 60 days postpartum. Our main analysis will include the full sample of women regardless of postpartum Medicaid coverage after 60 days, but we will also examine the outcomes in the subgroup of women who retained coverage for 24 months postpartum. If we find evidence that NFP affected average Medicaid enrollment or the type of woman enrolling in Medicaid, we will place more emphasis on the 6-week contraception outcomes when Medicaid coverage loss is minimal and more likely to be balanced between groups. Alternatively, if we find little evidence of differential coverage loss at 12 and 24 months, we will consider contraception outcomes at all three time points.

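### The contraception comparison among women who kept Medicaid for 24 months conditions on a post-randomisation variable that NFP may change, and the SAP plans checks for this but no bounds.

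*SAP*

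**What the plan says.** Section 3.5 of SAP Addendum 3 states the problem itself. Outpatient contraception cannot be seen for women outside Medicaid, and the section gives the reason for concern as "Because NFP may affect maintenance of Medicaid coverage past 60 days postpartum, including maintenance of enrollment in Medicaid Family Planning coverage". It adds that average enrollment could be equal while "the type of women retaining coverage will be affected by NFP". Continuous coverage is defined as "enrollment during all months, starting with the month of childbirth through 6 weeks, 12 and 24 months postpartum".

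The plan then has four parts:

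- The main analysis uses all women, whatever their coverage after 60 days.
- In addition, the outcomes are to be examined in the "subgroup of women who retained coverage for 24 months postpartum". No condition is attached, and neither the time points nor the type of coverage is named.
- Coverage is compared by arm, and the characteristics of enrolled women are compared with a joint F-test.
- If NFP appears to have affected coverage, more weight goes to the 6-week outcomes. If there is little sign of it, all three time points are considered.

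Addendum 2, section 2.1, leaves open a similar restriction for child preventive care: "we may restrict the sample to mother-baby dyads where children retain either partial or continuous Medicaid coverage".

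In Addendum 1 (Antenatal health), the SAP meets a comparable difficulty: care can be measured only in pregnancies that last long enough. There, if gestational age differs significantly by arm, "we will conduct a bounding exercise as a robustness check for the guideline-concordant care outcomes". Section 3.5 has no counterpart.

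**The concern.** Women who keep coverage for 24 months are a group formed after assignment. If NFP keeps some women enrolled who would otherwise have lapsed, the retained NFP women and the retained control women are different kinds of women, and their contraception rates can differ with no effect of NFP on contraception. Two features add to this. For a 12-month outcome, retention to 24 months is decided after the outcome window closes. Also, coverage of any type as defined for the coverage comparison includes the pregnancy pathway, so a repeat pregnancy, which contraception prevents, could itself keep a woman enrolled.

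The full-sample analysis has a different weakness. A woman who first obtains a method as an outpatient after losing Medicaid leaves no claim. If coverage differs by arm, so does the chance of being seen.

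Five of the eight outcomes in Table 3.2 have 12- or 24-month follow-up. If the two analyses disagree there, the plan gives the reader no interval that allows for the unobserved women.

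**Working it through.** The documents give no retention rate, contraception rate or power for this comparison, so there is no stated figure to reproduce. What follows is illustration under assumed rates.

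**1. What can the coverage comparison exclude?** Inputs: 3,295 NFP and 1,637 control mothers with an index birth (SAP Addendum 4, Table 3; an approximation, because the Addendum 3 sample also includes fetal deaths) and a two-sided 0.05 test (Protocol 5.1). Control retention p is assumed.

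At p = 50% against 53%, the standard error is √(0.50×0.50/1637 + 0.53×0.47/3295) = 0.0151. Then 0.03/0.0151 = 1.985, and power is Φ(1.985 − 1.960) = 51%.

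Over p = 20 to 70%:

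| True difference in retention | Power |
|---|---|
| 2 points | 26–36% |
| 3 points | 51–67% |
| about 3.5–4.2 points | 80% |

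At 50% retention in both arms, an observed difference of zero would still have a 95% interval of ±1.96 × √(0.25/1637 + 0.25/3295) = ±3.0 points. Little evidence of a difference is thus compatible with 2 to 3 points.

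**2. Retained-coverage comparison, no true effect on contraception.** Let d be the extra retention caused by NFP, a the contraception rate in women retained either way, and m the rate in women retained only because of NFP. The bias is d(m − a)/(p + d).

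- With a = 60%, p = 30%, d = 10 points and m − a = −30 points: 0.10 × (−0.30)/0.40 = −7.5 points.
- With p = 70%, d = 2 points and m − a = −10 points: 0.02 × (−0.10)/0.72 = −0.3 points.
- For d = 2 to 3 points, p = 30 to 70% and gaps of 10 to 30 points, the bias is −0.3 to −2.7 points, and a nominal 5% test rejects in about 5 to 18% of trials.
- With equal average retention but 5 to 20% of retained NFP women replaced by women whose rate is 10 to 30 points lower, the bias runs from 0.05 × 0.10 = 0.5 to 0.20 × 0.30 = 6 points downward.

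The sign reverses if the extra or replacing women have higher rates.

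**3. Full-sample contrast.** If NFP raises coverage by d, use is u, and all use outside coverage is missed, the contrast shifts by d × u: 0.02 × 0.40 = 0.8 points to 0.10 × 0.60 = 6 points. This is close to an upper range for those inputs, because the 12-month outcomes are cumulative and a claim made before coverage lapsed still counts. If half of users had such a claim (assumed), the range is 0.4 to 3 points.

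**4. What bounds would give.** In each arm let r be the share with a qualifying claim, and g the share with no qualifying claim whose coverage ended within the window.

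- None received: r_T − r_C.
- All received: (r_T + g_T) − (r_C + g_C).
- Opposite by arm: from r_T − (r_C + g_C) to (r_T + g_T) − r_C, of width g_T + g_C.

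The first two differ only by g_T − g_C. They nearly coincide when coverage loss is equal, even if different women are lost in the two arms. Only the opposite-by-arm pair covers that case.

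**The case against.** The strongest reply is that section 3.5 exists to deal with this. It discloses the threat, keeps the full sample as the main analysis, adds the retained group only as a supplement, and compares both coverage and characteristics. Section 3.2.2 brings in hospital discharge data to pick up inpatient provision. The Addendum 3 primary outcome, a birth interval under 21 months, comes from vital records and does not depend on Medicaid at all. All of that stands, and it limits the weight of the point. It does not supply a correction: the checks can show a problem, the F-test sees only measured characteristics, and the stated response is a change of emphasis.

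A reader might infer more than the text supports:

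- That the SAP expects NFP to change coverage. It says only that NFP may, and it plans for both outcomes of the check.
- That women without coverage are coded as non-users. No coding rule is given; the section says only that their outpatient use cannot be observed.
- That the 0.8 to 6 points measures bias in the retained group. It concerns the full-sample contrast only.
- That Lee bounds would settle the matter. They require NFP to move retention in one direction for every woman, which is doubtful when pregnancy and family-planning coverage could move in opposite directions. With equal average retention they trim nothing and return the retained-group estimate.

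For child preventive outcomes the restriction is optional, and section 2.5 plans its own checks, so the point applies there only if the restriction is used.

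**Conclusion.** The point holds in a limited form. The retained-coverage comparison is a supplementary analysis of non-primary outcomes, and it cannot be read as an effect of NFP. The full-sample analysis is free of that selection but open to unequal capture of first outpatient use after coverage ends. Neither weakness is corrected by the planned checks, and a non-significant coverage difference does not rule out one of 2 to 3 points.

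The size of either bias is unknown. The figures rest on assumed retention, coverage differences and contraception rates, and the direction in the retained group could go either way. It would go too far to call the 12- and 24-month outcomes uninterpretable: that is not shown, and how informative they are depends on how many women lose coverage without an earlier qualifying claim.

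**What to change.** In SAP Addendum 3, section 3.5:

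1. Keep the full-sample analysis as main.
2. State that the result in women retained for 24 months is descriptive and not an estimate of a treatment effect.
3. For the binary 12-month claims outcomes, and for any 24-month outcome expressed as receipt by 24 months, treat women with no qualifying claim who lost coverage as unobserved. Report the all-received and none-received versions, as in the Antenatal health subsection of Addendum 1, together with the opposite-by-arm worst case in line with the missing-outcome reference cited there.
4. Report these bounds whatever the coverage comparison shows.
5. Lee bounds may be added as a secondary analysis, with the monotone-retention assumption stated and a note that they do not address a change of composition at equal average retention.
6. Apply the same to child preventive outcomes if the optional restriction in Addendum 2, section 2.1, is used.

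The cost is a few extra analyses on data already planned for. The bounds may be too wide to be informative where coverage loss is heavy. Addendum 4 describes the trial manuscripts as published or forthcoming, so for some outcomes the bounds may have to appear in a later report; section A.2 already allows analyses to be revisited as records are updated.

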### **3.6. Subgroups**

Our primary sub-group is described in McConnell et al. (2020). Briefly, this subgroup comprises women who have an indicator of poor mental health, are under 19 years of age, or have not completed high school/received a General Education Development certificate by the time of enrollment.

In addition to the planned subgroup described above, we may also consider several other potential subgroups. We are interested in focusing more narrowly on groups who are most likely to benefit from increased access to family planning including teens, because pregnancies in this subgroup are more likely to be unintended than among adult women, and women who reported at baseline that they did not want to have another birth for at least two years. We are also interested in focusing on births that took place at least 24 months before the start of the COVID-19 pandemic (defined here as March 23, 2020). We expect that the pandemic altered the way that the NFP program was implemented. In addition, it is likely that the pandemic affected the availability of contraceptive services, fertility preferences, and employment; all factors on the causal pathway between NFP and birth outcomes.

---

 Medicaid and CHIP Income Eligibility Limits for Pregnant Women, 2003-2020. KFF. Published April 1, 2020. Accessed January 7, 2021. <https://www.kff.org/medicaid/state-indicator/medicaid-and-chip-income-eligibility-limits-for-pregnant-women/>

 Medicaid, Children's Health Insurance Program, & Basic Health Program Eligibility Levels | Medicaid. Accessed January 7, 2021. <https://www.medicaid.gov/medicaid/national-medicaid-chip-program-information/medicaid-childrens-health-insurance-program-basic-health-program-eligibility-levels/index.html#footnote1>

 Medicaid Income Eligibility Limits for Parents, 2002-2020. KFF. Published April 1, 2020. Accessed January 15, 2021. <https://www.kff.org/medicaid/state-indicator/medicaid-income-eligibility-limits-for-parents/>

#### Addendum 4: *Machine Learning Approach to Heterogeneity*

This Addendum was prepared and submitted February 5, 2025. At the time of the submission of this addendum, the analyses described in this addendum had not yet been performed.

Policymakers have looked to the expansion of intensive nurse home visiting programs to improve outcomes and address economic, racial and ethnic disparities. In recent decades, community implementation of nurse home visiting at scale has faced several challenges including patient retention, prioritization of nurse resources, and difficulties addressing sensitive topics including family planning and mental health. Research has called for the development of methods to prioritize resources in home visiting by targeting them toward families that are most likely to benefit. Home visiting services target based on a wide and heterogeneous range of potential risk factors from adolescent pregnancies to mental health challenges to substance use experiences. However, existing studies have been too small in size and scope to yield generalizable findings about which families should be prioritized to maximize the impact of home visiting.

Our trial context provides an important opportunity to understand heterogeneity of impact of home visitation among a large and diverse cohort of Medicaid eligible first-time mothers and their children participating in nurse home visiting. We will use a causal forests approach to identifying groups that most benefit from home visiting. We will collaborate with [name] and [name], who have implemented these methods in collaboration with [name] on experimental data from the Oregon Health Insurance Experiment (Inoue et al., forthcoming).

#### **Outcomes**

Our analysis will focus on pre-registered primary outcomes and indices of secondary outcomes derived from 8 manuscripts that are either published or forthcoming reporting on trial results (birth outcomes, prenatal outcomes, family planning outcomes, postpartum outcomes, mental health outcomes, social service outcomes and child outcomes). These indices will be created using the method developed by Kling, Liebman and Katz (2017). More sophisticated indexing techniques, such as the Optimus index developed by Anderson and Magruder (2023) will also be explored. These outcomes are specified in Table 4-10 with indications of whether participating in NFP would be expected to increase or decrease the outcome. For outcomes related to the use of the emergency department, participation in NFP might be expected to either increase the outcome (i.e. by identifying health challenges that need immediate attention) or decrease the outcome (i.e. by offering a trusted source of information that can reduce unnecessary care-seeking). We include an additional index of ED related outcomes in Table 11.

We will also consider exploratory analyses within the treatment group to determine whether characteristics that predict program outcomes overlap with those that predict program

participation. In this analysis the outcomes will be the number of home visits completed and the duration of participation in the program.

### **Predictors of Impact**

We will consider three different ways of assessing which type of population most benefits from home visiting within our trial. We do this by defining three different “sets” of family characteristics as follows. First, we consider an analysis that acknowledges that policymakers looking to target home visiting resources may be constrained to readily observable and objectively measurable characteristics. These observable characteristics are defined in Table 1 (the “Observable Characteristics” set). Second, we will conduct an analysis that considers how the impact of home visiting varies based on the extent of families’ social risk factors. Many home visiting programs and referral networks are built around the strong sense that “more vulnerable” families – defined as those with overlapping social risk factors -- are most likely to benefit from intensive home visiting services. However, there is also an increasing recognition that the same families at risk for more adverse outcomes may also be those who are less able to sustain participation in the program across the recommended timeline of nearly three years. We conducted a comprehensive literature review to identify social risk factors that have been acknowledged by home visiting programs or other early life interventions programs. The identified risk factors are defined in Table 2 (the “Social Risk Factors” set), including the sources used to identify these risk factors. The prevalence of each of the risk factor in our study sample is presented in Table 3. Finally, we will consider a comprehensive set of baseline covariates including all information collected about families at baseline, using continuous versions of baseline covariates whenever possible (the “Full Covariate” set). These covariates will be derived from the survey conducted with pregnant women during their enrollment in the study (see [Additional file 5](#) of the published study protocol). We will perform causal forest analysis for all three sets of covariates. We will also perform more traditional heterogeneity analysis with the Social Risk Factors assuming that the risk factors are additive and considering whether the treatment is more impactful for those with more social risk factors.

**Table 1. Observable Risk Factors**

	Definition	Sources
Under 18	Estimated date of delivery falls before respondent's 18th birthday	Darling et al., 2024 (young); Cavallaro et al., 2022; Catherine et al., 2020 ( $\leq 19$ ); Foulon et al., 2015 ( $\leq 19$ ); Stamuli et al., 2015 (young)
Living in high poverty area	Zip code of residence is census tract poverty rate $\Rightarrow 25\%$	Darling et al., 2024 (disadvantaged area; low-income); Tereno et al., 2022 (low-income); Catherine et al., 2020 (receiving income assistance, finding it difficult to live on total household income regarding food or rent, homeless); Haire-Joshu et al., 2019

		(home zip code associated with median household income below poverty level); Foulon et al., 2015 (low socioeconomic status); Stamuli et al., 2015 (financial difficulties; living in a very deprived area)
Have not completed high school	Has fewer than 12 years of completed education (less than high school education)	Darling et al., 2024; Tereno et al., 2022; Catherine et al., 2020; Foulon et al., 2015
Food insecurity	Responded sometimes or oftentimes to either question: "Worried food might run out before got money to buy more, "Food didn't last and didn't have money to buy more"	Catherine et al., 2020

